11.0 Specimen Collection and Banking

Videotapes will be stored for future use, by Drs. [name] and [name] in a password protected file on the pediatric server, behind MUSC's firewall. Future use will include education and teaching sessions and in presentations to describe the combined CIMT and taVNS treatment. They will be deidentified as much as possible although the therapist may use the infant's name during CIMT. Only Drs. [name], [name] and [name] and study personnel will have access to subject identities. Only coded identifiers will be used to store and link to videotapes. If parents wish to withdraw the infant videotapes at any age prior to 18 years, they may request to do so in writing, and withdraw any future use of the child's videotape.

Videotapes will not be released to other parties not directly involved in research.

12.0 Data Management

Analysis and Statistical plan: We will compare the change in score on functional measures between CIMT+ taVNS via repeated measures ANOVA from pre- to immediately and 30 days post- treatment via ANOVA. Power analysis on primary outcome is not valid with 5 participants. However, for reference in infants treated with 60 vs 120h intensive CIMT⁸, the QUEST grasp mean changed from 4.50 ± 2.6 to 5.25 ± 3.1 with 3h/day CIMT ($\Delta=0.75$), versus 4.14 ± 2.6 to 5.73 ± 3.0 with 6h/day CIMT ($\Delta=1.59$). We estimate 40h of CIMT+taVNS, 2h/day CIMT+taVNS will be similar to 3h CIMT, Δ grasp =0.75.⁸

Keeping Data Confidential: We will assign study numbers to each participant, keep CRF and consent forms in locked offices. Database files with names and contact information will be password protected and stored on the MUSC Pediatric server. All other data files related to this study will be identified by participant number only, without link to standard identifiers. We will publish the aggregate data only.

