4.0 Study Endpoints

Primary Research Question: Can taVNS stimulation be automatically triggered during 75% of the total time for active infant arm and trunk movements during CIMT? **Primary Outcome measure:** Percentage of treatment sessions where total stimulation time was 75% of total active movement time.

Limitations and alternative approaches: *Trialing EMG system:* We will trial the EMG sensor system first with two healthy infants in the CHP laboratory setting to trouble shoot set-up and connection issues. The BSL and CIMT team will make any necessary modifications to the EMG-taVNS set-up. *Comparing total movement time to total stimulation time does not ensure stimulation is being provided at the appropriate time:* The stimulation device changes color when stimulation is being provided. Therefore, a second 'recording' therapist can monitor if the screen is green('on') when also recording active movement.

Aim 2: To generate proof of concept evidence demonstrating ability to provide high fidelity CIMT+taVNS treatment in a home-based setting in 3 infants. We will have a second therapist videotape CIMT therapy sessions while the CIMT therapist is delivering taVNS in the home with EMG triggered taVNS. We will randomly score 20% of sessions for CIMT treatment fidelity with published CIMT Fidelity tool. This aim will be completed with the final 3 participants after EMG set-up is finalized with first 2 participants.

Secondary CIMT+taVNS feasibility outcomes: Ability of therapist to operate taVNS easily and successfully by earning a "meet or exceed" score (3 or 4) on random therapy sessions by CIMT Fidelity Instrument. Ability of infant to tolerate wired ear electrode while remaining securely in place during sessions.

Secondary CIMT +taVNS efficacy outcomes: Change in the functional motor outcomes pre and post intervention on the *Quality of Upper Extremity Skills Test (QUEST)*

Title: Extending taVNS Paired with Infant CIMT into a Home-Based Setting: Technology Development Requisite for a Randomized Trial

PI: [name]

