5.0 Inclusion and Exclusion Criteria/ Study Population

Inclusion Criteria: Five 6–18 month-old infants, with hemiplegia/motor asymmetry qualifying for CIMT, Gross Motor Function Classification System (GMFCS) level I-IV, ability to maintain sitting position for 5 minutes with moderate assistance.

Exclusion Criteria: GMFCS level V, severe motor impairment/ quadriplegic involvement; uncorrected blindness or deafness, cardiomyopathy.

6.0 & 7.0 Number of Subjects and Setting

We will enroll up to 5 infants. The first two infants will complete all study intervention procedures in the pediatric occupational therapy lab ([name]). This will allow for monitoring by the whole team and minor modifications to be made to the set-up (adjusting placement of EMG sensors, adding Velcro to keep wires out of the way when reaching, etc). Image from on-going taVNS +CIMT study (without EMG triggering).

This new study should only require minor changes to the set-up (adding wires for EMG muscle sensors). After completing 2 infants in the lab which should provide more than enough opportunity to modify set-up issues. The remaining 3 participants will complete study interventions in their home. A specially trained pediatric therapist will deliver all treatment sessions. A second study team member will also accompany the therapist to assist with therapy, video tape sessions, and monitor the infant.

Figures 1 & 2. CIMT therapist assists infant's trunk control while the trigger button is attached to her hand with flexible wrap (red arrow). taVNS device is Velcro attached to the infant's back (green arrow). The arm with better motor skill is immobilized with red flexible wrap and a splint.

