The parents of infants who present for CIMT are highly motivated, and willing to commit to the time and effort commitment for CIMT. Most of the study procedures occur during the active treatment period. Therefore, we anticipate >95% retention to completion of the immediate outcome measures. For the 3 months follow-up assessment, we will call every month to discuss infant progress with the mother/caregiver. All of these infants will also have regular developmental follow-up in MUSC's or other high-risk clinic, and we will collect this data with parent consent, though it is not part of the primary or secondary outcomes for the phase I trial.

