10.0 Study Design / Methods

Title: Extending taVNS Paired with Infant CIMT into a Home-Based Setting: Technology

Development Requisite for a Randomized Trial

PI: [name]

Overall Study Design: The goal of this discovery pilot project is to further develop the technical aspects of taVNS+CIMT delivery so that it is practical for delivery by a CIMT therapist in a home-based setting. This is essential to prepare for a treatment effectiveness study, which by necessity must be home-based because of the minimum 40-hour time commitment. First, we will use EMG sensors to automatically trigger the taVNS device, with the goal of decreasing the burden of treatment for the therapist. We will place the EMG sensors on major muscle groups on the shoulder and trunk and refine placement as needed to show that EMG-triggering can accurately and effectively trigger stimulation for 75% of total time spent in active movements. The therapist will still be able to manually trigger for other targeted behaviors (such as grasping). Once our placement of sensors has been tested and meets this designated threshold, the EMG-triggered system will be tested in home-based CIMT treatment.

This study will determine the feasibility of using EMG sensors to trigger taVNS stimulation paired with CIMT therapy in n=5, 6-18month old infants with hemiplegia after perinatally acquired brain injury. We will measure the effect of active taVNS paired with 40 hours of CIMT on infant motor skills before and after treatment over a month, and follow up the motor skills over 3 months. All infants will receive active taVNS treatment. CIMT treatment is a non-research procedure, and motor and developmental testing are non-research procedures. taVNS is a research procedure. CIMT sessions will be videotaped, to measure the fidelity of CIMT delivery while the therapist is delivering taVNS to determine feasibility.

The alternative treatment is the usual and customary occupational therapy services. If parents wish, they may pursue CIMT therapy with local therapists, but there are very few qualified therapists in the area. Also, although CIMT is considered a gold standard intervention, it is often not covered by insurance due to the time intensity required.

We will monitor for and mitigate following risks are present with this study: Risk of skin irritation, risk of discomfort, risk of slightly decreased heart rate, and risk of loss of confidentiality.

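### The repeated-measures ANOVA planned for the secondary motor outcome does not estimate the pre-to-post change and, in its usual complete-case form, would discard observed pre/post pairs when the later score is missing

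*Combined protocol and SAP*

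**What the plan says.** Section 4.0 lists the motor outcome as a secondary efficacy outcome: "Change in the functional motor outcomes pre and post intervention", measured with the QUEST. The primary outcome is the percentage of sessions meeting the 75% stimulation-time criterion, and the analysis discussed here does not touch it.

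The only analysis stated for the motor outcome is one sentence in Section 12.0, which compares change in score "via repeated measures ANOVA from pre- to immediately and 30 days post- treatment via ANOVA". The section names no estimate, confidence interval or rule for missing scores. It concedes that "Power analysis on primary outcome is not valid with 5 participants". It then gives reference figures, among them that "the QUEST grasp mean changed from 4.50 ± 2.6 to 5.25 ± 3.1 with 3h/day CIMT", and concludes: "We estimate 40h of CIMT+taVNS, 2h/day CIMT+taVNS will be similar to 3h CIMT", meaning an expected grasp change of 0.75.

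On size and design, Section 6.0 & 7.0 says "We will enroll up to 5 infants" and Section 10.0 says "All infants will receive active taVNS treatment", so there is no comparator. On retention, Section 8.0 says "we anticipate >95% retention to completion of the immediate outcome measures". For the later assessment it offers monthly calls but no figure. Section 14.0 continues motor follow-up after early termination only for infants who stay with the department. The later assessment is at 30 days in Section 12.0, but Sections 8.0 and 10.0 speak of 3 months.

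**The concern.** There are two mismatches between the outcome and its analysis.

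First, the outcome is a pre-to-post change, and a later randomised trial would need the size of that change and its uncertainty. An overall F test over three occasions asks only whether any of the means differ. Whether significant or not, it does not give the size of the change.

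Second, classical repeated-measures ANOVA is normally run on complete rows. An infant who misses only the later visit would then leave the pre-to-immediate comparison as well, although both scores needed for it were observed. Each of five infants is 20% of the data. The later visit is the one most exposed to loss: the plan gives no retention figure for it, its timing is inconsistent, and Section 8.0 notes that some families travel great distances.

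**Working it through.** **Inputs from the documents.** n is up to 5 (Section 6.0 & 7.0). Reference QUEST grasp means (SD) from Section 12.0 are 4.50 (2.6) to 5.25 (3.1) at 3 h/day and 4.14 (2.6) to 5.73 (3.0) at 6 h/day. The expected change is 0.75.

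**Assumptions not in the documents.** Pre-post correlation r of 0.5 to 0.9; two-sided 5% level; loss at the later visit of 5% to 20%, independent between infants.

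**1. The plan's own figures.** 5.25 − 4.50 = 0.75 and 5.73 − 4.14 = 1.59. Both reproduce. The plan states no sample-size or power calculation to check.

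**2. Cost of losing an infant.** The 95% half-width for a mean paired change is t(0.975, n−1) × SD of change / √n. The multiplier of the SD is:
- n = 5: 2.7764/√5 = 1.242
- n = 4: 3.182/√4 = 1.591, and 1.591/1.242 = 1.28
- n = 3: 4.303/√3 = 2.484, and 2.484/1.242 = 2.00

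For a given SD of change, these ratios do not depend on r.

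**3. Precision against the expected change.** SD of change = √(2.6² + 3.1² − 2r × 2.6 × 3.1) = √(16.37 − 16.12r).

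| r | SD of change | Half-width, n = 5 | n = 4 | n = 3 |
|---|---|---|---|---|
| 0.5 | 2.88 | 3.58 | 4.59 | 7.16 |
| 0.7 | 2.26 | 2.80 | 3.59 | 5.60 |
| 0.9 | 1.36 | 1.69 | 2.17 | 3.39 |

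With all five infants and an observed mean change of exactly 0.75, the interval runs from −0.94 to 2.44 at r = 0.9 and from −2.83 to 4.33 at r = 0.5. Both contain 0 and 1.59. Excluding zero would need an SD of change below 0.75/1.242 = 0.604, that is r above (16.37 − 0.604²)/16.12 = 0.993.

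**4. Is the ANOVA to blame for the imprecision?** Power for a change of 0.75 at n = 5:
- Repeated-measures ANOVA (noncentral F on 2 and 8 df, compound symmetry, common SD 2.9, change of 0.75 at both later occasions): about 7%, 9% and 18% for r = 0.5, 0.7 and 0.9.
- Paired t-test: about 7%, 9% and 16%.

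The two are nearly the same, so the weakness comes from n = 5.

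**5. How likely is an incomplete infant?** The chance that at least one of five lacks the later score is 1 − (1 − d)⁵: 23% for d = 5%, 41% for d = 10%, 67% for d = 20%.

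**The case against.** A reader might infer that the ANOVA will lose the pre-to-post result. The documents do not support that. They nowhere state complete-case deletion; it is the usual behaviour of the named method. An ANOVA with infant and time as factors can be fitted to incomplete rows. The loss is conditional on a missed score, and the monthly calls and the continued follow-up in Section 14.0 may reduce it.

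A reader might also infer that the ANOVA is why the change is poorly estimated. Steps 3 and 4 show otherwise: the wide half-widths belong to the paired interval itself.

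Nor does the plan test whether its result resembles the 3 h/day figure or differs from the 6 h/day figure. It offers 0.75 as an estimate, for reference. The outcome is secondary in a feasibility pilot, and the plan concedes that power analysis is not valid with five infants, although it says so of the primary outcome. The analysis sentence is also loosely worded: it could mean two separate changes from baseline, and nothing in it forbids reporting means.

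These points limit the concern but do not remove it. Under either reading the plan names no interval and no missing-score rule, and its usual implementation would discard pairs that bear directly on the stated outcome.

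**Conclusion.** The point holds as an inexpensive improvement to a secondary analysis. The stated method does not deliver the quantity Section 4.0 defines, and in its usual form it makes the pre-to-immediate comparison depend on a visit that comparison does not need. If one infant is lost this way the interval for the mean change is 28% wider, and if two are lost it doubles. Those ratios rest only on the t distribution and n, for the same SD of change.

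The statement that five infants cannot confirm or refute a grasp change of 0.75 rests on the plan's SDs and the assumed correlation of 0.5 to 0.9, which give half-widths of about 3.6 to 1.7 points. That imprecision is due to n = 5 and remains after the fix. The probability of an incomplete infant rests on assumed loss rates, because the documents give none for the later visit.

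**What to change.** In Section 12.0:

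- Make the main motor result the mean paired QUEST change from pre to immediate-post with a 95% t-interval, using every infant who has both scores.
- Report the change from pre to the later visit separately in the same way.
- Treat any p-value as descriptive.
- State that five infants cannot confirm or refute the expected grasp change of 0.75.
- Reconcile the later assessment time with Sections 8.0 and 10.0, since it determines which score can be missing.

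This takes a few lines and no new data. The downside is that the ANOVA F test is no longer the main motor result.

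A coded per-infant listing would suit five infants but is optional. It would need the commitment to publish only aggregate data to be amended in Sections 10.0, 12.0 and 15.0, with thought given to re-identification in so small a group and to the confidentiality assurance in Section 13.0.

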13.0 Provisions to Monitor the Data to Ensure the Safety of Subjects

Data and Safety Monitoring Plan

Title: Extending taVNS Paired with Infant CIMT into a Home-Based Setting: Technology Development Requisite for a Randomized Trial

PI: [name]

The participants who receive active taVNS involved with this proposal will be infants whose participation is agreed to by their parent/guardians in written consent. The principal investigator will be responsible for monitoring the safety of the proposed experiments. [name] and [name] will also execute the Data Safety Management (DSM) plan and provide any necessary progress reports to the IRB, including but not limited to subject demographics, recruitment rates, retention rates, quality assurance issues, and adverse events or significant adverse events. [name] or her designee, should she be unavailable, will be responsible for reporting all unanticipated problems or AEs to the IRB. The PI or Co-I will be present for patient visits and the OT Research Assistant will discuss any perceived AE with them. [name] will be responsible for reporting any unanticipated device- related AE's to FDA. All screening data will be kept in a binder in [name] locked office. Screening data collected from participants who do not qualify for the study will be securely destroyed.

[name], who is a board-certified neurologist and psychiatrist, and [name] will oversee the use of the taVNS system. [name] will be immediately available to the RA to monitor safety and adverse events.

An independent Safety Monitoring Committee (SMC) will be formed to advise the study investigators. The SMC will review and evaluate accumulated study data to ensure safety, as in the pilot trial. They also will make recommendations concerning continuation, modification, or termination of any of the taVNS studies. It will be composed of [name] PT PhD and NM4R PI, [name], OT PhD; and [name], MUSC associate professor psychiatry and assistant provost with extensive VNS, TMS, and tDCS experience. The SMC and IRB will be notified immediately of any and all SAE's.

Drs. [name], [name] and [name] will obtain informed consent for mother and infant to participate, during which participants' guardians are fully advised on the research procedures to be used, the amount of time required of them, the possible risks and benefits of the procedures, their right to refuse their infant's participation in the study without prejudice, their right to terminate participation of their infant at any moment without prejudice, and the name and telephone number of the principal investigator.

Regarding confidentiality, subjects' guardians are informed that the information they provide, as well as participation in the study, will be kept strictly confidential, with access limited to the research staff. All paper records (consents, CRFs, study tools) will be kept in [name] locked office in the College of Health Professions. The identity of subjects in databases will be protected with alphanumeric codes. All data will be kept in locked office or on secure servers designed for use and access by Brain Stimulation and Neonatology, and OT Lab members only.

Title: Extending taVNS Paired with Infant CIMT into a Home-Based Setting: Technology

Development Requisite for a Randomized Trial

PI: [name]

14.0 Withdrawal of Subjects

Parents may withdraw their infants at any time. Reasons may include excessive demands of time for CIMT or family pressures. Infants may be withdrawn without parental consent, if taVNS is poorly tolerated. If either occur, parents will be referred for clinical CIMT, or if this is not possible within the parent's home structure, other occupational and physical therapy as appropriate. We will continue to collect follow-up data on motor skills even with early termination, if infants continue with MUSC OT department.

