8.0 Recruitment Methods

We have IRB approval for two pilot studies (#67997, #103800) in preterm and term stroke/HIE infants with taVNS paired with feeding using similar taVNS study procedures as proposed in this application. The taVNS system has a non-significant risk device designation from MUSC's IRB in these two pilot trials.

[name] will screen for infants in the nursery with known brain injury that will likely lead to hemiparesis or weakness, such as perinatal arterial stroke, HIE, severe IVH, PVL or cerebellar infarct, regardless of sex or race. The clinical team will inform the parents of the potential to

Title: Extending taVNS Paired with Infant CIMT into a Home-Based Setting: Technology

Development Requisite for a Randomized Trial

PI: [name]

participate in the study. [name] will then explain the study to the parents and give them contact information if they are interested, to initiate screening and consent procedures when their infant reaches 6-8months of age. Infants are also referred directly to [name] and [name] specifically for CIMT from a wide region of the southeast. Because some parents travel great distances to get these services, we may obtain referrals from other care providers out of our region. We will perform phone screening and obtain Econsent prior to patient arrival for patients whose parents cannot meet in person prior to the first treatment session, to be able to get services fully prepared for the visit. We will use the approved REDcap system to obtain consent. [name] or other approved study personnel will go over the entire consent document on the phone with the parent to ensure comprehension and to confirm identity. Parent will be given a copy of the completed, signed consent form in person or by email or fax.

Volunteers of all ethnicities and racial categories will be accepted into this study protocol. No preference will be given based on race, gender or ethnicity. Young infants who had perinatal complications leading to perinatally acquired brain injury may be considered vulnerable populations and are the target of this proposal.

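### Section 14.0 ties motor follow-up after early stopping to staying with the local OT department, so an infant who moves care can be lost from the secondary QUEST outcome without any withdrawal of consent

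*Combined protocol and SAP*

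**What the plan says.** Section 14.0 sets a condition on motor data after early termination: "We will continue to collect follow-up data on motor skills even with early termination, if infants continue with MUSC OT department". It gives two routes to stopping. Parents may withdraw the infant: "Reasons may include excessive demands of time for CIMT or family pressures". The study may also stop the infant: "Infants may be withdrawn without parental consent, if taVNS is poorly tolerated". In either case the family is referred to clinical CIMT or, if that is not workable, to "other occupational and physical therapy as appropriate". Neither referral is tied to the local department.

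Section 8.0 expects some families to come from far away: "Because some parents travel great distances to get these services, we may obtain referrals from other care providers out of our region". It anticipates more than 95% retention to the immediate outcome measures and gives no figure for the later assessment. For that it plans telephone contact: "For the 3 months follow-up assessment, we will call every month to discuss infant progress with the mother/caregiver". It also plans to collect developmental data from the local or another high-risk clinic with parental consent, but places these data outside the primary and secondary outcomes.

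Section 4.0 makes QUEST change a secondary efficacy outcome. The primary outcome is the percentage of sessions that meet the 75% stimulation-time threshold. Section 12.0 plans a repeated measures ANOVA of the functional measures and states no analysis set and no rule for missing values. On sample size, the section on number of subjects says: "We will enroll up to 5 infants".

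**The concern.** This is a stated rule rather than a gap in the text. Whether a stopped infant is assessed again depends on who provides later therapy, and the plan's own referral route can take the infant out of the department on which the rule depends. An infant stopped by the study for poor tolerance is the clearest case: the parent has not refused anything and might willingly return for a QUEST, yet the rule does not provide for one if care has moved.

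Such a loss is avoidable, and it could be related to outcome. An infant who stops has received less of the 40-hour programme, and poor tolerance is a reaction to the study treatment. At stake is how completely the motor change describes the infants who started treatment. In a sample this small, one missing infant matters for both the mean and its precision.

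**Working it through.** **Inputs.** Sample size of up to 5, taken as 5 (section on number of subjects). Expected QUEST grasp change of 0.75 (Section 12.0). Anticipated retention above 95% (Section 8.0). The change in a lost infant, d, is not in the documents, so every value of d below is an assumption.

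**The plan's own figure.** Section 12.0 cites grasp means of 4.50 before and 5.25 after: 5.25 − 4.50 = 0.75, as stated.

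**Share of the data.** One infant of five is 1/5 = 20%. Retention can only be 100%, 80%, 60% and so on, so retention above 95% means that nobody is lost. If each infant independently had a 95% chance of being retained (an assumption), the chance of losing at least one would be 1 − 0.95^5 = 1 − 0.774 = 0.226. This is the chance of any loss, not of loss through this rule, which needs an infant both to stop and to leave the department.

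**Effect on the mean.** Suppose four assessed infants average 0.75 and one unassessed infant changes by d. The reported mean is 0.75, the mean of all five is (4 × 0.75 + d)/5, and the difference is (0.75 − d)/5.

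| Assumed d | Mean of all five | Reported minus all five |
|---|---|---|
| 1.50 | (3.00 + 1.50)/5 = 0.90 | −0.15 |
| 0.75 | (3.00 + 0.75)/5 = 0.75 | 0 |
| 0.375 | (3.00 + 0.375)/5 = 0.675 | 0.075 |
| 0 | (3.00 + 0)/5 = 0.60 | 0.15 |
| −0.75 | (3.00 − 0.75)/5 = 0.45 | 0.30 |

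The sign of the difference depends wholly on d.

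**Effect on precision.** The half-width of a 95% t-interval for a mean change is t(0.975, n−1)/√n in units of the SD of change. For n = 5 it is 2.776/2.236 = 1.24 SD; for n = 4 it is 3.182/2 = 1.59 SD. This cost arises whatever the direction of any bias.

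**Whether other text closes the gap.** The monthly calls discuss progress; they are not QUEST assessments and are not stated to continue after withdrawal. The clinic data are outside the outcomes. A classical repeated measures ANOVA drops any infant with a missing time point, and Section 12.0 says nothing to the contrary. No other section removes the condition.

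**Which assessments are meant.** Sections 8.0 and 10.0 describe follow-up to 3 months, while Section 12.0 analyses the immediate and 30-day points. As written, it is unclear which QUEST assessments a stopped infant would miss.

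**The case against.** The case for leaving the text alone has substance.

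- The condition concerns the place of later care, not response. Time demands and family pressures are about the family, and poor tolerance is about ear stimulation; no section links any of these to motor gain. This stands. A reader might infer that the rule keeps the infants who did well and so overstates benefit, but the documents do not support that.
- Section 8.0 says only that out-of-region referrals may occur. It does not say that such families would leave the local department. All five infants must be reachable on five days a week for four weeks, which makes loss at the immediate assessment less likely. This also stands; it limits how often the rule will bite but does not remove it.
- Section 10.0 classes motor testing as a non-research procedure, which plausibly explains why follow-up was tied to a clinical department. This bears on the cost of the change, not on whether data are lost.
- The motor result is weak evidence in any case. With an assumed SD of change between 0.5 and 3 points, the 95% half-width at n = 5 runs from 1.24 × 0.5 = 0.62 to 1.24 × 3 = 3.7 points, larger than any shift in the table. This stands, and it is why the point is minor.
- Section 14.0 is already more generous than ending all data collection at withdrawal. True, and removing the condition completes that intention.

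**Conclusion.** The point holds as a cheap improvement, not as a flaw that threatens the study. Section 14.0 can leave a stopped infant out of the secondary QUEST outcome for a reason unrelated to consent, and each such infant is 20% of a sample of five. The loss could be related to outcome. Its direction and size are unknown, and the shift of 0.15 (0.75 reported against 0.60) rests on an assumed zero gain in the lost infant.

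Two further inferences should be resisted. One is that a distorted QUEST mean would be carried into planning the next trial: Section 1.0 rests the future grant application on the refined home protocol and reliable triggering, and Section 12.0 quotes QUEST change for reference while declining a power analysis. The other is that the main result is compromised: the primary outcome is counted over treatment sessions, and this rule does not affect it.

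**What to change.** In Section 14.0, delete the condition about continuing with the local department. State instead that every infant who starts treatment will be invited to the already planned post-treatment and follow-up QUEST assessments at the study site, whoever provides later therapy, unless the parent withdraws consent to follow-up.

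In Section 12.0, report individual QUEST changes for all infants who started, identify the completers, and give the reason and time of each stop. Reconcile the 3-month follow-up in Sections 8.0 and 10.0 with the 30-day analysis in Section 12.0, so that the required assessments are clear, and say from which date they are counted for an infant who stopped early. The monthly calls and clinic records can serve as supporting information but not as a replacement for QUEST scores.

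The cost is a few sentences and one or two visits for a family that stopped early. Some families will decline, particularly those who stopped because of time. Because Section 10.0 treats motor testing as non-research, the team should check that an assessment outside ongoing local care is covered by the consent and by study resources. Treatment, eligibility and the primary outcome are unchanged.
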